6.2.17.1 Procedures and documentation

For all premature terminations/discontinuations, the Investigator will document the primary reason and relevant details in the eCRF (dropout/discontinuation form). Where appropriate, the case will be discussed with the Sponsor. If feasible, and if the participant and parents agree, an early termination visit will be performed to capture key outcome assessments and to collect information on adverse events/serious adverse events up to the time of discontinuation.

6.2.17.2 Handling of data and missing assessments (interval-censored primary endpoint)

Data collected prior to discontinuation will be retained and used in analyses in accordance with applicable law and the scope of consent. If consent for use of data is withdrawn, previously collected data will be handled in accordance with regulatory requirements (e.g., retention of essential safety data where required) and the participant's stated wishes.

The primary endpoint (time to radiographic healing) will be analyzed as an interval-censored time-to-event outcome. For participants with radiographs demonstrating "not healed" followed by "healed," the event time will be considered to occur within the interval between the date of the last radiograph showing "not healed" and the date of the first radiograph showing "healed."

If a participant has no radiograph demonstrating healing, the observation will be right-censored at the date of the last evaluable radiograph/assessment.

If a participant undergoes reoperation, experiences refracture, or otherwise has a clinical course that precludes further valid assessment of healing, follow-up will be censored at the date of the last evaluable radiograph prior to that event, unless the event is pre-specified as a competing event in the Statistical Analysis Plan.

Assumptions and handling of missing radiographs (including sensitivity analyses for potentially informative missingness) will be pre-specified in the Statistical Analysis Plan.

6.3 Study treatments

All study treatments are provided according to standard of care and in accordance with the applicable Technique Guide for each implant system. Treatments are considered as standardized treatment packages consisting of either:

- surgical treatment with bioabsorbable intramedullary nails (BIN) and casting for 4 weeks, or
- surgical treatment with titanium elastic intramedullary nails (TEN) and casting for 2 weeks.

This is a randomized controlled study. Randomization procedures are described below.

6.3.1 Device under investigation

The investigational medical device (IMD) in this study is the Activa IM-Nail™ (Bioretec Ltd., Tampere, Finland), a sterile, single-use, bioabsorbable intramedullary nail intended for intramedullary fixation of pediatric diaphyseal forearm fractures (radius and/or ulna) in the presence of appropriate immobilization.

6.3.1.1 Device identification (IMD)

- Device name / brand: Activa IM-Nail™
- Size range: diameters 2.0–3.2 mm; lengths 200–400 mm
- Key material characteristics (high-level): bioabsorbable polymer-based nail with a radiopaque marker (as described in the Investigator's Brochure/IFU).
- Degradation (high-level): biodegrades in a controlled manner within approximately two years.

6.3.1.2 Regulatory status and conformity (high-level)

- The device is CE-marked; design examination certification for Activa IM-Nail is issued by DEKRA Certification B.V. (Notified Body 0344), certificate 2094913DE05.
- The manufacturer's Declaration of Conformity and applicable quality system certification references are provided as appendices.
- Continued placing on the market and putting into service under the MDR transitional provisions is documented by the manufacturer (including applicability to Activa IM-Nail and stated end of transition period for bioabsorbable implants).

6.3.1.3 Use in this clinical investigation

The Activa IM-Nail™ will be used within its intended purpose and according to the manufacturer's instructions (Technique Guide/IFU). No modifications to the device or deviations from its intended purpose are planned.

6.3.1.4 Traceability and device accountability

To ensure traceability, the following will be recorded in the eCRF (and/or device accountability log): device name, catalogue/reference number (REF), and batch/lot number (LOT). Device labeling and essential regulatory documentation are retained in the Investigator Site File (ISF).

Supporting documentation (submitted as EC appendices; not repeated in the protocol text)

Detailed device description, intended purpose, contraindications/warnings, technical characteristics, pre-clinical and clinical evidence summaries, and conformity documentation are provided in:

- Investigator's Brochure (Activa IM-Nail™ Product Group)
- EC Design-Examination Certificate (DEKRA) 2094913DE05
- Declaration of Conformity (Class III devices)
- Manufacturer's Declaration regarding MDR transitional provisions (EU 2023/607)
- Essential Requirements Checklist

6.3.2 Comparator

The comparator device in this study is the Titanium Elastic Nail (TEN™) System (DePuy Synthes). The TEN™ system is a commercially available, CE-marked orthopedic trauma implant system used to perform elastic stable intramedullary nailing (ESIN) for stabilization of pediatric long-bone fractures, including pediatric diaphyseal forearm fractures. The TEN™ system is not investigational in the context of this clinical investigation and will be used within its approved intended use/indications and according to the manufacturer's Instructions for Use (IFU) and Surgical Technique.

The TEN™ system consists of flexible titanium alloy intramedullary nails supported by dedicated instrumentation for implantation and extraction. The nails are available in multiple diameters and lengths suitable for pediatric forearm fracture fixation (e.g., 1.5 mm × 300 mm and 2.0–4.0 mm × 440 mm).

Device traceability will be ensured by recording the device name and relevant identifiers (e.g., article number, and where applicable sterile/non-sterile designation and packaging identifiers) in source documentation and the eCRF/device accountability documentation, in accordance with local procedures. Detailed technical specifications, labeling, indications/contraindications, warnings, and handling instructions are provided in the appended TEN™ documentation (IFU/Surgical Technique/Investigator's Brochure) submitted to the Ethics Committee.

6.3.3 Constancy and assay sensitivity of the reference treatment (TEN)

Noninferiority inference in this trial relies on the assumption of constancy (assay sensitivity), i.e., that the active control intervention (TEN) would be expected to achieve its established effectiveness under the conditions of the present study.

The trial is therefore designed to maintain close similarity to the evidence base supporting TEN for pediatric diaphyseal forearm fractures with respect to (1) the enrolled population (age range, fracture location and pattern, displacement, and operative indication), (2) the conduct of the reference intervention (TEN performed according to manufacturer guidance and local standard practice by appropriately experienced surgeons, with standardized key perioperative and postoperative care pathways), and (3) outcome definitions and follow-up schedule (radiographic healing assessed using prespecified, operational criteria and prespecified time points).

Any clinically relevant differences from the studies underpinning TEN effectiveness (e.g., case-mix, perioperative regimen, immobilization practice, or outcome timing/definition) will be described and justified in the final trial report, and adherence to the planned delivery of TEN and follow-up will be monitored to support assay sensitivity.

6.3.4 Treatment, surgical technique and postoperative care

All operative and non-operative management is performed according to standard of care and in accordance with the manufacturer's Technique Guide/IFU for the relevant implant. Operational details are described in the corresponding site SOPs.

Procedures are performed under general anesthesia (GA) with the patient in the supine position and the injured arm positioned on a radiolucent arm table. GA may be supplemented with a peripheral nerve block (PNB) in accordance with local standard practice [40].

6.3.4.1 Closed reduction pathway (prior to randomization)

Where applicable, an attempt at closed reduction is performed before skin incision.

- If closed reduction is achieved and the fracture no longer meets criteria for surgical stabilization, a circumferential above-elbow cast is applied, and alignment is confirmed with intraoperative radiographs. If alignment is satisfactory, surgery is cancelled, and the participant is managed as part of the non-operative cohort (Section 6.3.8).
- If closed reduction is not applicable, unsuccessful, or the fracture remains irreducible and/or unstable, the participant proceeds to randomization (Section 6.3.5).

6.3.4.2 Operative pathway (randomized treatment packages)

Participants randomized to surgical treatment will undergo intramedullary fixation using either:

- BIN package: bioabsorbable intramedullary nail fixation with casting for 4 weeks, or
- TEN package: titanium elastic intramedullary nail fixation with casting for 2 weeks.

The operative technique for the two interventions is largely identical, with implant-specific steps performed according to the relevant Technique Guide. In brief, intramedullary canal access is established and the nail is advanced under fluoroscopic guidance; fracture reduction is performed closed where feasible, with open reduction permitted if required. Postoperative radiographs are obtained.

Antibiotic prophylaxis will be administered according to local standard practice (weight-based dosing). In case of penicillin allergy, an appropriate alternative will be used per local guidelines.

6.3.4.3 Postoperative care and discharge

Wounds are closed and dressed according to standard practice. A circumferential above-elbow cast is applied for the duration specified by the randomized treatment package. Discharge occurs when the child is clinically well and postoperative pain is controlled, typically on the same day or the day after surgery, in accordance with local routines. No formalized physiotherapy is routinely prescribed; participants and parents receive oral and written instructions regarding mobilization and home exercises.

Follow-up assessments are conducted according to the schedule described in Section 6.2.

6.3.5 Allocation to study groups

Allocation will be 1:1 between the investigational (BIN) and comparator (TEN) groups, stratified by age.

6.3.6 Randomization process

- The participant must meet all inclusion criteria and none of the exclusion criteria, and written informed consent from parents must be obtained.
- Randomization will be performed in the operating room (OR) with the participant under general anesthesia (GA) if closed reduction is not applicable or is unsuccessful (i.e., the fracture remains irreducible and/or unstable and surgical stabilization is indicated).
- A delegated member of the research team will randomize the participant to treatment with either BIN or TEN.
- Randomization will be conducted using the REDCap Randomization module with age stratification.
- Contingency plan: If REDCap is temporarily unavailable, randomization will be performed using a predefined, access-restricted backup procedure (e.g., sealed opaque envelopes or a pre-generated randomization list) as described in the corresponding SOP, and the allocation will be entered into REDCap as soon as system access is restored.

6.3.7 Blinding

Blinding is implemented to minimize performance and assessment bias [41–43]. Due to the nature of the interventions, the operating surgeon and operating room staff cannot be blinded to implant type.

Allocation is concealed from participants, parents, postoperative clinical staff, outcome assessors, and the statistician. A limited number of designated study personnel (e.g., PI and trial coordinator) are unblinded to facilitate device logistics and, when relevant, planning of elective titanium nail removal; these personnel will have no role in postoperative assessments, radiographic outcome evaluation, or data analysis.

Participant and parent unblinding will occur only after completion of the 6-month follow-up assessment, primarily to enable planning of elective removal of titanium nails in accordance with standard practice. All outcome assessors and the statistician will remain blinded until database lock and completion of the primary analysis, unless unblinding is required for patient safety.

6.3.7.1 Blinded postoperative documentation

To maintain blinding of participants, parents, and routine postoperative caregivers, a standardized “blinded” postoperative documentation pathway will be used in the electronic health record (EHR). The purpose is to prevent inadvertent disclosure of treatment allocation through operative notes, discharge documentation, or follow-up scheduling, while ensuring that complete and legally compliant source documentation is retained and remains available to authorized clinical staff when needed.

Immediately after surgery, documentation will be split into:

- Blinded postoperative note (visible to routine postoperative care and to families via patient-facing portals, where applicable): A standardized template will be used stating that the participant “underwent intramedullary fixation with one of the two study nails according to randomization,” without naming implant type. The note will include study information (including emergency contact information), non-allocating clinical essentials (diagnosis, reduction status, approach, complications, cast applied, neurovascular status, activity restrictions, analgesia plan, and safety advice).
- Additional operative record (restricted access): An additional operative record containing the implant type, sizes, lot/batch identifiers, and any implant-specific technical details will be completed and

retained as source documentation with access restricted to authorized staff (e.g., operating surgeon, delegated unblinded study personnel, and clinicians requiring access for safety). Implant traceability information (REF/LOT, sizes) will also be recorded in the device accountability log/eCRF as prespecified.

6.3.7.2 *Maintaining blinding despite imaging and clinical routines*

For research outcome assessment, postoperative radiographs will be exported as de-identified copies and edited to conceal implant-specific radiopaque features as described in Section 7.1. Clinical care will continue to rely on unedited radiographs in the medical record. Study staff involved in follow-up assessments will avoid disclosure of allocation, and participants and parents will be asked not to seek information on implant type until after the 6-month visit.

6.3.7.3 *Emergency unblinding*

Unblinding may be performed only when knowledge of the allocated implant is deemed necessary for urgent clinical management. Emergency unblinding will be performed by the PI, documented in the eCRF (date, reason, person unblinded, and who was informed), and reported to the sponsor.

6.3.7.4 *Blinded groups*

The following parties will be blinded to treatment allocation:

- Participants and parents will be blinded to implant type. Families will be informed preoperatively that postoperative immobilization duration may vary between 2–4 weeks based on radiographic assessment, and they will not be informed that immobilization duration differs systematically between the randomized interventions. As the implant is not externally visible after cast removal and implant-specific radiographic features are concealed for research assessments (Section 7.1), there is no direct method for participants and parents to identify allocation during follow-up.
- Postoperative ward/clinic caregivers and staff involved in routine care.
- Outcome assessors and data collectors, including:
 - Clinicians performing follow-up assessments
 - Radiologists and orthopedic surgeons reviewing radiographs (using edited, de-identified images; Section 7.1)
 - Occupational therapists / hand therapists performing functional assessments
- Statistician/data analyst, who will receive a dataset with groups coded (e.g., Group A/B) and will remain blinded until database lock and completion of the prespecified primary analysis.

6.3.7.5 *Preventing inadvertent unblinding*

To reduce inadvertent disclosure, the study team will implement the following safeguards:

- Use of standardized note templates for postoperative notes and discharge summaries.
- Clear instruction to staff not to document implant type in routine follow-up notes that are accessible to blinded parties.
- If implant type must be referenced for clinical reasons before planned unblinding, it will be documented and handled according to the emergency unblinding procedure.

6.3.7.6 *Assessment of blinding success*

Blinding success will be assessed immediately prior to participant/parent unblinding at the 6-month follow-up visit. Participants/parents will be asked to guess the allocation (“bioabsorbable”, “titanium”, or “don’t know”) and if they specify an implant, they will be asked why they chose that implant. The proportion of correct guesses and reasons (and proportion choosing “don’t know”) will be summarized by randomized group.

6.3.8 **Postoperative care**

Following surgery, a circumferential above-elbow cast is applied. The patient will be observed and/or admitted to the pediatric ward as clinically indicated until the effect of the peripheral nerve block (PNB) has subsided and discharge criteria are met. The patient is encouraged to mobilize the shoulder and fingers as soon as possible and to keep the arm elevated for the first few days. Daily activities may be resumed as tolerated. Return to sports will be discussed individually at the 3-month follow-up visit in accordance with standard of care.

Before discharge, a standardized discharge and follow-up plan will be provided.

In the investigational group (BIN), all patients will remain in a cast for 4 weeks. In the comparator group (TEN), cast removal is planned at the 2-week follow-up visit.

Any postoperative care not specifically described in this protocol will be provided according to standard of care at the study site and described in a specific SOP.

6.3.9 **Non-operative treatment**

If the fracture is successfully reduced by closed manipulation prior to skin incision and is considered eligible for non-operative management, the patient will be included in an exploratory prospective non-operative cohort. Based on our pilot experience, the proportion of successful closed reductions is anticipated to be approximately 15%.

6.3.9.1 *Eligibility for non-operative management*

Fractures are considered eligible for non-operative treatment when, after reduction, the fracture is:

- not displaced by more than 50% of the bone width, and
- not angulated by more than 10° in any plane.

The decision to manage the fracture non-operatively is at the treating surgeon’s discretion and follows standard of care.

6.3.9.2 *Follow-up and conversion to surgery*

Participants in the non-operative cohort will have a radiographic follow-up at 1 week. Thereafter, they will follow the same follow-up schedule and outcome assessments as the randomized groups (Section 6.2). Fracture healing is typically sufficient to allow cast removal after 6–8 weeks.

If, during subsequent follow-up no later than 14 days after injury (e.g., at the planned 1-week non-operative control), loss of reduction occurs such that the fracture again meets the study’s operative indication criteria, the participant remains eligible for the randomized comparison. In this situation, the participant will follow the standard pathway and be randomized in the operating room immediately prior to surgery, using the trial’s randomization procedure (Section 6.3.5).

The period of initial non-operative management and the indication for conversion to surgery will be documented.

Any subsequent re-intervention or conversion to surgery occurring later than 14 days after injury will be recorded and analyzed descriptively.

7 Definitions of outcome measures and study variables

This study adheres to the CORE-Kids core set of outcome domains described by Marson et al. [44].

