7.1.1.4 Blinding of radiographs via standardized image masking

Bioabsorbable intramedullary nails are largely radiolucent, with only a radiopaque tricalcium phosphate tip, whereas titanium nails are inherently radiopaque. To ensure blinded radiographic outcome assessment across treatment groups, all postoperative radiographs will be de-identified and digitally masked prior to review. Using image-editing software, visible radiopaque implant components will be concealed, while preserving full visibility of the fracture region, cortical outlines, and callus formation (Figure 3). All patient identifiers and acquisition metadata will be removed, and images will be assigned a study-specific ID and a non-revealing time point label only.

Image manipulation will be performed by a member of the research team who is not involved in postoperative clinical assessment, outcome evaluation, or statistical analysis, and who will have no role in adjudication of radiographic endpoints. Masking procedures will be documented to ensure consistency. All manipulated images are stored outside PACS. All original unaltered radiographs are stored in the hospital's PACS.

Original follow-up radiograph

Edited radiograph with implant concealed

Figure 3 – Example of original and edited radiograph to blind the assessor to the implant.

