7.2.6.1 Re-fracture, re-displacement, or re-angulation

At each FU the radiographs are reviewed for occurrence of re-fracture, re-displacement, or re-angulation. If changes are below the boundaries described in the inclusion criteria in 6.1.1 no additional treatment is necessary. If the boundaries are exceeded the PI and the surgeon will discuss the need for additional treatment.

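### Follow-up clinicians are declared blinded, but unedited films and arm-specific cast removal reveal the implant, so blinding of clinician-assessed secondary outcomes is not secured

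*Protocol*

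**What the plan says.** Section 6.3.7.4 of the protocol lists the blinded parties. Under assessors and data collectors it names "Clinicians performing follow-up assessments", and as a separate item "Postoperative ward/clinic caregivers and staff involved in routine care". Section 6.3.7 sets how long this lasts: "All outcome assessors and the statistician will remain blinded until database lock and completion of the primary analysis", with an exception for patient safety.

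Section 6.3.7.2 provides edited, de-identified copies of the films for research reading only, and adds: "Clinical care will continue to rely on unedited radiographs in the medical record". Section 7.1.1.4 explains why editing is needed: the bioabsorbable nail (BIN) is largely radiolucent apart from its tip, "whereas titanium nails are inherently radiopaque". On complications, section 7.2.6.1 says: "At each FU the radiographs are reviewed for occurrence of re-fracture, re-displacement, or re-angulation".

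Cast time is part of each treatment package (sections 6.3 and 6.3.4.2). Section 6.3.8 says: "In the investigational group (BIN), all patients will remain in a cast for 4 weeks". For the titanium (TEN) arm it plans removal at the 2-week visit. Families, however, are to be told that "immobilization duration may vary between 2–4 weeks based on radiographic assessment" (section 6.3.7.4), and are not told that the duration differs systematically by arm.

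**The concern.** The staff declared blinded seem to be the staff who look at unmasked films and take casts off on an arm-specific schedule. If so, range of motion (ROM), grip, deformity and radiographic complications are recorded by people who know the implant, while the report of a trial titled multi-blinded would present them as blinded. These outcomes leave room for judgement: how far to push a joint before reading the goniometer, how much to encourage a grip effort, whether to record a deformity or a re-angulation. The surgeons cannot be blinded and the study team may well have a view on the new implant, so the declared protection matters. A reader of the results could not see that it was missing, because section 6.3.7.6 tests blinding only in children and parents.

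**Working it through.** The point rests on no statistical calculation, so the check sets the sections side by side.

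1. **Who is blinded, and for how long.** Sections 6.3.7 and 6.3.7.4: follow-up clinicians and clinic staff in routine care. Outcome assessors stay blinded until database lock.

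2. **What an unedited film shows.** Section 7.1.1.4: metal nails are visible and BIN nails largely are not. One postoperative film identifies the arm.

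3. **Who sees unedited films.** Section 6.3.7.2 keeps clinical care on them. Section 6.3.7.4 mentions edited images only for the radiologists and orthopedic surgeons who read films for research. Table 1 and section 7.3 schedule films at 2, 4, 6 and 12 weeks, 6 months, 1 year and 2 years, and at 8 and 10 weeks where needed. Section 7.2.6.1 has films reviewed at each of these visits. The material that reveals the arm is therefore present at every visit.

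4. **Who must act on the arm.** Section 6.2.6 (2 weeks) lists radiographs, cast removal for the TEN group, and the clinical examination and outcome assessments together. Section 6.2.7 (4 weeks) does the same with cast removal for the BIN group. Whoever carries out those lists has to know which children are due.

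5. **How strongly cast time marks the arm.** Section 8.3.3.1 makes a cast duration more than 7 days off plan a major deviation, unless medically indicated and documented.
   - TEN: 14 ± 7 days, i.e. day 7 to day 21.
   - BIN: 28 ± 7 days, i.e. day 21 to day 35.
   - The two windows meet only at day 21. Among children treated to plan, cast time practically identifies the arm for anyone who has read the protocol. Cast status stops being a visible cue once both casts are off; the film does not.

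6. **What safeguards exist.** Sections 6.3.7.1, 6.3.7.2 and 6.3.7.5 provide neutral note templates, an instruction not to disclose allocation and a rule against recording implant type. These limit what staff say and write, not what they see.

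7. **Are the roles separated elsewhere?** Section 7.2.10 gives the instruments for ROM and grip but not the person who measures. Section 6.3.7.4 lists therapists doing functional assessments as blinded, but the visit lists name an occupational therapist only for the motor test, at 12 weeks (6.2.11) and 24 weeks (6.2.12). No section keeps the person who measures away from films and casts.

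8. **What lies outside the contradiction.** The primary endpoint is read on masked films by two independent blinded reviewers, with a third to adjudicate (7.1.1.5). Pain on the FPS-R is the child's own report (7.2.3.1).

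**The case against.** The strongest reply is that no section says the same person views the film, removes the cast and measures the outcome. Operational detail is left to site SOPs, which are not shown, and the listed therapists might already measure ROM and grip. That stands as a limit on wording: the documents show that blinding is contradicted and not secured, not that it is absent for every measurement. It does not remove the point, since routine clinic staff as a group are declared blinded while their care runs on unedited films.

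A reader might infer more than the text supports:
- **Pain is unblinded.** The FPS-R is self-report, so a clinician's knowledge does not by itself unblind it.
- **The decision on further treatment is wrongly presented as blinded.** Section 7.2.6.1 gives it to the PI and the surgeon, both of whom section 6.3.7 already treats as unblinded.
- **The 8- and 10-week visits are triggered by someone who knows the implant.** Sections 6.2.8 and 6.2.9 tie them to mRUS below 11 and name no reader. It is possible, but not stated.
- **Early ROM and grip differences due to cast time show a failure of blinding.** Cast time belongs to the packages compared (section 6.3), so perfect blinding would leave that difference in place.
- **Families should leave the blinded list, or the title is false.** The contradiction concerns staff. Nothing in it shows that family blinding fails, and several parties remain blinded.

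**Conclusion.** The point holds in this form: the statement that follow-up clinicians and clinic staff are blinded conflicts with sections 6.2.6, 6.2.7, 6.3.7.2, 6.3.8 and 7.1.1.4. Blinding is not secured for the clinician-assessed secondary outcomes: ROM, grip, deformity, and the radiographic complications reviewed at visits. Films expose the arm at every follow-up visit, and the cast schedule does so as well at weeks 2 and 4.

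The direction and size of any resulting bias cannot be derived from the document. No sample size, margin or primary-analysis figure changes, and the masked primary reading is not called into question.

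The conclusion assumes that clinic staff see the films used for clinical care and that no unseen SOP separates the roles. If an SOP does, the protocol should say so and the defect shrinks to wording. Apart from that, what families are told about cast time disagrees with the arm-fixed durations whatever the SOPs contain.

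**What to change.** - In section 6.3.7.4, list as unblinded the clinicians who view unedited films or remove casts. Label the outcomes they record as open-label in section 7.2 and in the report.
- Have ROM and grip at 12 weeks measured by the occupational therapist who is already scheduled for the motor test, under a written rule of no access to films or allocation and no questions about cast time. Make that the blinded between-arm comparison. By then both planned cast periods are over and families have not yet been told the implant.
- Extend this to 24 weeks only after the therapist visit is settled: section 6.2.12 lists it, whereas Table 1 and section 7.2.10.1 place the motor test at 12 weeks only.
- Reconcile the statement to families in section 6.3.7.4, that cast time depends on the radiographs, with the arm-fixed durations in sections 6.3 and 6.3.8. This review takes no view on which cast rule is right.

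The cost is protocol wording and a few minutes in an existing therapist session. The drawback is that fewer secondary outcomes can be reported as blinded.
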